10.9.4.4 Pharmacokinetic Data

Not applicable.

10.9.4.5 Pharmacodynamic Data

Immunogenicity will be assessed using the Immunogenicity Set and will be repeated for the Per Protocol Set, should the analysis sets differ.

Antibody Response: Antibody titre responses (IgG concentrations [specific for GBS-NN and GBS-NN2]) will be listed along with the Day 1 and Day 85 results obtained from the MVX0002 study. Antibody response data will be summarised descriptively using N, geometric mean and 95% confidence interval (CI) for the geometric mean, , minimum, median, maximum and IQR (interquartile range), by study (MVX0003, MVX0002) and dose level received in the MVX0002 study (placebo/vaccine naïve, 25ug, 50ug) and active doses pooled. Individual and geometric mean plots of antibody concentrations will also be produced by study and dose level received in the MVX0002 study.

In order to explore the decline in IgG antibodies since the previous study, a statistical comparison of the GBS-NN and GBS-NN2 antibody concentrations on Day 1 of the MVX0003 study and Day 85 of the MVX0002 study will be performed for each of the corresponding MVX0002 dose levels and active doses pooled. Following logarithmic transformation, antibody concentrations will be subjected to a mixed effect analysis of variance (ANOVA), with study as a fixed effect and participant as a random effect. Point estimates and 95% confidence intervals will be constructed for the contrasts between Day 1 (MVX0003) and Day 85 (MVX0002). The point and interval estimates will be back-transformed to give estimates of the ratios of the geometric least squares means (LSMeans) and corresponding 95% CIs for each MVX0002 dose level and all active doses pooled.

A similar ANOVA will also be performed in order to compare the Day 85 GBS-NN and GBS-NN2 antibody concentrations for the MVX0003 study to those obtained for the MVX0002 study, for each of the corresponding MVX0002 dose levels and all active doses pooled.

Additionally, the GBS-NN and GBS-NN2 antibody concentrations observed on Day 85 of the MVX0003 study will be compared between participants who received 25ug GBS-NN/GBS-NN2 in the previous study and placebo/vaccine-naïve participants, between participants who received 50ug GBS-NN/GBS-NN2 in the previous study and between placebo/vaccine-naïve participants and the participants who received either active dose (25ug and 50ug pooled) in the previous study and placebo/vaccine-naïve participants. Following logarithmic transformation, Day 85 antibody concentrations will be subjected to an analysis of variance (ANOVA), with dose level as a fixed effect. Point estimates and 95% CIs will be constructed for the contrasts between the dose levels. The point and interval estimates will be back-transformed to give estimates of the ratios of the geometric LSMeans and corresponding 95% CIs.

The fold-increase in antibody concentrations specific for GBS-NN and GBS-NN2 will be derived between:

- Day 1 and Day 85 for both the MVX0002 and MVX0003 studies, for each of the corresponding MVX0002 dose levels and all active vaccines pooled.
- Day 85 of the MVX0002 study and Day 85 of the of the current MVX0003 study, for each of the corresponding MVX0002 dose levels and all active vaccines pooled.

Fold-increases will be listed and descriptive statistics (N, n, geometric mean and corresponding 95% CI, minimum, median, maximum and IQR) will be tabulated by study and MVX0002 dose level and all active vaccines pooled.

In addition, the proportion of participants with concentrations above the pre-determined thresholds of 1, 2, 4 and 8 µg/mL at Day 85 will be presented by study and MVX0002 dose level and all active vaccines pooled.

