10.4.1 Inclusion Criteria

To be confirmed at Screening:

1. Women who have participated in study MVX0002, with GBS-NN/NN2 vaccine and received active vaccine or placebo (unless it is necessary to recruit vaccine naïve participants to bolster the number of participants who received placebo in MVX0002).
2. Able to voluntarily provide written informed consent to participate in the study.
3. Healthy female participants aged 18-40 years (vaccine naïve participants only).
4. Female participant of childbearing potential willing to use a highly effective method of contraception (in addition to a condom for male partners), if applicable (unless of non-childbearing potential or where abstaining from sexual intercourse is in line with the preferred and usual lifestyle of the participant) from the first dose until completion of the Day 85 visit. A woman is considered of childbearing potential, i.e. fertile, following menarche and until becoming post-menopausal unless permanently sterile. Permanent sterilisation methods include hysterectomy, bilateral salpingectomy and bilateral oophorectomy. *For the purposes of this study, this definition of a female of childbearing potential applies to all females in the study i.e., those who participated in the MVX0002 study and those who are considered vaccine naïve.*
5. Female participant of non-childbearing potential. *For the purposes of this study, this is defined as the participant being at least 4 months post-surgical sterilisation (including bilateral fallopian tube ligation or bilateral oophorectomy with or without hysterectomy).*
6. Female participant with a negative pregnancy test at Screening and prior to dose.
7. Female participant of menopausal status confirmed by demonstrating at Screening that the serum level of the follicle stimulating hormone (FSH) falls within the respective pathology reference range. In the event a participant's menopausal status has been clearly established (for example, the participant indicates she has been amenorrhoeic for 10 years, confirmed by medical history, etc), but serum FSH levels are not consistent with a postmenopausal status, determination of the participant's eligibility to be included in the study will be at the Investigator's discretion following consultation with the Sponsor.
8. Body mass index (BMI) ≥ 18 and ≤ 30 kg/m² (vaccine naïve participants only).
9. Participants' weight ≥ 50 kg and ≤ 100 kg at Screening (vaccine naïve participants only).

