10.9.5 Sample Size Calculation

Sample size calculation has not been assessed. It is limited by the number of participants who have participated in study MVX0002 and are willing to participate for this study. A minimum of 30 and a maximum of 40 female participants will be recruited, comprised of between 20 and 30 participants who had received previous vaccination with GBS-NN/NN2 in the MVX0002 study and up to 10 participants who had received placebo in the MVX0002 study. If an insufficient number (<5) of previous placebo recipient participants return to this study, vaccine naïve participants will be recruited.

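### If new naïve women are recruited, the placebo-stratum cross-study ratios in Protocol 10.9.4.5 become partly a comparison of different women

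*Protocol*

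**What the plan says.** Section 10.9.4.5 of the Protocol summarises antibody concentrations by study and by "dose level received in the MVX0002 study (placebo/vaccine naïve, 25ug, 50ug", with the active doses also pooled. This is the section's only list of what the MVX0002 dose levels are.

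Two cross-study models follow.

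- **MVX0003 Day 1 against MVX0002 Day 85.** It is introduced with the words "In order to explore the decline in IgG antibodies since the previous study". The comparison "will be performed for each of the corresponding MVX0002 dose levels and active doses pooled". On the log scale the model is a "mixed effect analysis of variance (ANOVA), with study as a fixed effect and participant as a random effect".
- **Day 85 against Day 85.** "A similar ANOVA will also be performed in order to compare the Day 85 GBS-NN and GBS-NN2 antibody concentrations" between the two studies, again by MVX0002 dose level and with active doses pooled.

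Neither description says what happens to a woman who has no MVX0002 value.

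Section 10.9.5 (also 10.1 and 10.4) explains how such women arise. The plan is for "up to 10 participants who had received placebo in the MVX0002 study", and "If an insufficient number (<5) of previous placebo recipient participants return to this study, vaccine naïve participants will be recruited". Section 8.2 makes clear that these recruits took no part in MVX0002.

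**The concern.** A newly recruited naïve woman has no MVX0002 dose level and no MVX0002 sample, so the merged label does not describe her. If the label carries over into the cross-study models, she contributes one MVX0003 value and nothing from MVX0002.

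A paired analysis would drop her. A model with a random participant effect does not: it uses her value to estimate the MVX0003 mean, and so takes some information from comparing her with the returning placebo women. The placebo-stratum ratio is meant to describe change over time in the same women. It would then also carry any difference in antibody level between two groups of women.

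The two groups are selected differently. Section 10.4.1 has "Healthy female participants aged 18-40 years (vaccine naïve participants only", and its BMI and weight limits are likewise for naïve women only. In Section 10.4.2, the case-by-case allowance for chronic medication is open only to former MVX0002 participants. At stake is the meaning of the placebo-stratum ratio in both models.

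**Working it through.** **Inputs from the Protocol.** Model: study fixed, participant random, log concentrations (10.9.4.5). New women enter only if fewer than 5 placebo recipients return, and the placebo group is planned at up to 10 (10.9.5). The Protocol gives no standard deviation, correlation or power for this analysis, so it has no figure to reproduce.

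**Assumptions, not in the Protocol.** Within-woman correlation rho between the two studies, and the log difference in level D between new and returning women. Values are varied below. The examples take 10 as the ceiling for the whole non-vaccinated group.

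**Is a mix of 4 returners and 6 new women possible?** The minimum enrolment is 30. With 20 previously vaccinated women, 30 − 20 = 10 others are needed, and 4 + 6 = 10. With 30 previously vaccinated women the minimum is already met, so fewer or no new women may be needed.

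**Formula.** Let p women have both values and m have MVX0003 only, with equal variances in the two studies. Generalised least squares gives:

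- MVX0003 mean = average of all p + m MVX0003 values
- MVX0002 mean = paired MVX0002 average + rho × (MVX0003 mean − paired MVX0003 average)

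If new women differ by D, the MVX0003 mean shifts by D × m/(p+m) and the MVX0002 mean by rho times that. The log study contrast is therefore biased by

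D × m/(p+m) × (1 − rho).

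**Numbers for an assumed 2-fold difference** (D = log 2, factor = 2 to the power of the weight):

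| p | m | rho | weight m/(p+m) × (1 − rho) | factor |
|---|---|---|---|---|
| 4 | 6 | 0.2 | 0.6 × 0.8 = 0.48 | 1.39 |
| 4 | 6 | 0.5 | 0.6 × 0.5 = 0.30 | 1.23 |
| 4 | 6 | 0.8 | 0.6 × 0.2 = 0.12 | 1.09 |
| 2 | 8 | 0.5 | 0.8 × 0.5 = 0.40 | 1.32 |
| 2 | 8 | 0.8 | 0.8 × 0.2 = 0.16 | 1.12 |
| 4 | 1 | 0.8 | 0.2 × 0.2 = 0.04 | 1.03 |

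The factor multiplies the ratio if new women have higher levels and divides it if lower. It is 1.00 when D = 0 or m = 0. With p = 0 there is no within-woman ratio and the contrast cannot be estimated in that stratum.

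**Check with estimated variances.** A 300-run REML simulation with p = 4, m = 6 and a 2-fold difference gave 1.21, 1.12 and 1.05 at rho 0.5, 0.8 and 0.9. The formula gives 1.23, 1.09 and 1.04. Some fits in such small samples had convergence trouble, so this is rough confirmation only. The paired-only estimate was 1.01 to 1.04, within simulation noise of 1.00.

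**Price of a paired-only rule.** The all-women variance divided by the paired-only variance is 1 − ½ × m/(p+m) × (1 − rho). For p = 4, m = 6 this is 1 − 0.15 = 0.85 at rho 0.5 and 1 − 0.06 = 0.94 at rho 0.8. The paired-only standard error is thus larger by 1/√0.85 = 1.08 or 1/√0.94 = 1.03.

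**The case against.** **The carry-over is inferred.** The merged label stands in the descriptive sentence, while the models refer to corresponding MVX0002 dose levels, which new women do not have. Where Section 10.9.4.5 wants naïve women in a contrast, as in the Day 85 between-group ANOVA, it names them. This is fair. But the section gives no other list of dose levels and no restriction, so including them is the natural reading.

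**It is detail for the SAP.** Handling of women with one value is often left there, and the SAP was not available for this point. It may already settle the matter. Still, the Protocol itself fixes strata, model and contrasts, and these together produce the mixed ratio.

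**The populations may hardly differ.** MVX0002 also enrolled healthy women aged 18 to 40 (8.4), and the medication restriction differs only by a case-by-case exception. This stands: a different selection route does not show a difference in antibody level, and the 2-fold figure has no anchor in the Protocol.

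**A stronger inference that does not hold.** A reader might conclude that the merging ruins the only internal check on assay shift between the studies, since placebo women should show a ratio near 1. The Protocol does not support this:

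- It gives the placebo stratum no such role; the stated aim is to explore decline.
- The Synopsis plans a fold-increase from MVX0002 Day 85 to MVX0003 Day 1, calculated per woman, so new women cannot enter it. Section 10.9.4.5 omits that item but still lists individual MVX0002 values beside the MVX0003 ones, so the paired ratio can be obtained.
- Section 8.2 attributes natural antibodies to GBS colonisation, so levels in placebo women can move over 1 to 5 years without vaccine or assay shift.

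**Conclusion.** The point holds as a minor defect of specification. As written, and on the natural reading, new naïve women enter the placebo stratum of both cross-study models and make its ratio partly a between-women comparison.

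It arises only if fewer than 5 placebo recipients return and new women are recruited. The size then depends on two quantities the Protocol does not give. Under an assumed 2-fold difference, the 4 + 6 mix gives a factor of 1.23 at rho 0.5 and 1.09 at rho 0.8; one new woman beside 4 returners gives 1.03 at rho 0.8. Rho may also differ between the models, because in the Day 85 model the MVX0003 value follows a vaccine dose and the MVX0002 value does not.

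The 25 µg, 50 µg and pooled-active ratios contain no naïve women and are untouched, so the findings on decline and booster response in vaccinated women do not depend on this. The primary objective is safety and is not involved.

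**What to change.** Add one sentence to Section 10.9.4.5, mirrored in the Synopsis and the SAP: both cross-study ANOVAs include only women with values in both MVX0002 and MVX0003, so that the placebo stratum consists of MVX0002 placebo recipients alone. Keep new naïve women in the MVX0003-only summaries and in the Day 85 between-group ANOVA, where merging them with placebo recipients fits the stated comparison.

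The cost is precision in one stratum. Where the problem arises, the placebo stratum has 4 or fewer women and a wider confidence interval (standard error up by about 8% at rho 0.5 and 3% at rho 0.8 in the 4 + 6 example, before the loss of degrees of freedom). No extra data, visits or assays are needed.

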10.9.4.6 Other Data

- Individual participant antibody concentration specific for AlpCN, RibN, Alp1N and Alp2-3N will be analysed and reported separately.
- Additional exploratory assessments for exploratory objectives including [REDACTED] results will be analysed and reported separately.

10.9.5 Sample Size Calculation

Sample size calculation has not been assessed. It is limited by the number of participants who have participated in study MVX0002 and are willing to participate for this study. A minimum of 30 and a maximum of 40 female participants will be recruited, comprised of between 20 and 30 participants who had received previous vaccination with GBS-NN/NN2 in the MVX0002 study and up to 10 participants who had received placebo in the MVX0002 study. If an insufficient number (<5) of previous placebo recipient participants return to this study, vaccine naïve participants will be recruited.

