| This is an open label vaccine booster follow-up study. Participants who had received a primary course of GBS-NN/NN2 or placebo in Study MVX0002 will be invited to return to receive a booster dose (or first dose in the case of placebo or vaccine naïve participants) 1 to 5 years after the completion of the primary course of vaccination. All participants will receive a single dose of GBS-NN/NN2 containing 50µg of each fusion protein. |

A minimum of 30 and a maximum of 40 female participants will be recruited, comprised of between 20 and 30 participants who had received previous vaccination with GBS-NN/NN2 in the MVX0002 study and up to 10 participants who had received placebo in the MVX0002 study. If an insufficient number of previous placebo recipient participants return to this study, vaccine naïve participants will be recruited.

The study will include 7 visits (Visit 1: Screening Period, Visits 2-6: Treatment Period and Visit 7: Post-study Follow-up).

Visit 1 - Screening Period (Day -28 to Day -1):

After signing the informed consent form, Screening assessments will be performed within 28 days of the planned dose to ensure the eligibility of participants. Screening assessments will include:

- Inclusion/Exclusion Criteria
- Demographic data
- Subject number and Investigational Medicinal Product received in MVX0002 study
- Medical history
- Physical examination (full)
- Height, weight and body mass index (BMI)
- Vital signs (supine heart rate, blood pressure, tympanic temperature and respiration rate)
- 12-lead ECG
- Virology (human immunodeficiency virus (HIV), hepatitis B surface antigen (HBsAg) and hepatitis C virus antibody (HCV Ab))
- Laboratory safety tests (biochemistry, haematology)
- Urinalysis
- Urine drugs of abuse including alcohol and cotinine
- Serum pregnancy test
- Follicle Stimulating Hormone Test (Postmenopausal women only)
- Prior and concomitant medication

Visits 2-6 - Treatment Period (Day 1 to Day 85):

Visit 2 (Day 1):

Participants will be admitted to the clinic in the morning of Day 1 and will remain in the unit until the 30 minutes (min) post-dose scheduled assessments. The following procedures will be performed on Day 1.

- COVID-19 Reverse Transcription Polymerase Chain Reaction Test: Pre-dose (can be performed at Visit 1, Day -1 at the discretion of the Principal Investigator (PI))
- Physical examination: Pre-dose (brief) and 30 min (\pm 5 min) post-dose (Symptom-Directed Physical Examination prior to discharge)

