10.4 Selection of Study Population

All women who have participated in Study MVX0002 with GBS-NN/NN2 will be re-contacted and invited to participate in this study. It is intended to recruit 20 to 30 women who have received a primary course of vaccination with GBS-NN/NN2 and up to 10 women who received placebo in the MVX0002 study. If insufficient (<5) participants who received placebo in Study MVX0002 return to this study, vaccine naïve participants will be recruited.

The following eligibility criteria are designed to select participants for whom protocol treatment and procedures are considered appropriate. All relevant medical and non-medical conditions should be taken into consideration when deciding whether this protocol is suitable for a particular participant.

Deviations from inclusion and exclusion criteria are not allowed as deviations have the potential to impact the scientific integrity of the study, regulatory acceptability or participant safety as such deviations constitute a deliberate breach of Regulation 29 of Statutory Instrument (SI) 2004/1031. Therefore, adherence to the criteria as specified in the protocol is essential.

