10.5.4 Removal of Participants from Further Assessment

Each participant will be informed of their right to withdraw from the study at any time and for any reason.

An Investigator may withdraw participants from the study at any time for any of the following reasons:

- If a participant experiences a serious or intolerable AE, that prevents them from continuing. Participants will be followed-up for safety and until resolution of the AE unless lost to follow-up.
- If a participant incurs a significant protocol violation which impacts on their safety or the scientific integrity of the study.
- At the request of the Sponsor.
- If it is considered that the participant's health is compromised by remaining in the study or the participant is not sufficiently cooperative.
- If a participant is lost to follow-up.
- Pregnancy before Day 85 (will be discussed with the participant and sponsor to establish continuation of monitoring required).

All cases will be discussed on a case-by-case basis with the sponsor. The decision and the reason for any participant withdrawal will be recorded on the study completion form of the electronic case report form (eCRF).

If a participant is withdrawn or chooses to withdraw from the study for any reason every possible effort will be made to perform the evaluations described for the post-study follow-up (see Table 10.7.1). The data collected from withdrawn participants will be included in the study report.

In the event of any abnormalities considered to be clinically significant, participants will be followed-up with appropriate medical management until values are considered to be clinically acceptable. Referral or collaborative care will be organised if considered necessary.

A minimum of 30 and maximum of 40 female participants are required to complete the study. Participants who withdraw from the study before receiving any IMP will be replaced if suitable reserves are available. Participants who are withdrawn from the study due to significant drug-related AEs will not be replaced. Replacement of all other participants withdrawn from the study after receiving IMP will be decided on a case-by-case basis by the Principal Investigator (or deputy) and Sponsor.

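### Does recruiting vaccine-naïve women when fewer than 5 placebo recipients return leave the trial short of its minimum of 30?

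*Protocol*

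**What the plan says.** Section 10.9.5 gives the total, "A minimum of 30 and a maximum of 40 female participants will be recruited", and its make-up, "comprised of between 20 and 30 participants who had received previous vaccination with GBS-NN/NN2 in the MVX0002 study" plus up to 10 MVX0002 placebo recipients. The same section says that no sample size calculation was made and that the number depends on how many MVX0002 participants are willing to return.

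The rule for adding vaccine-naïve women appears in two strengths:

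- With a threshold, in sections 10.1 and 10.9.5 ("If an insufficient number (<5) of previous placebo recipient participants return to this study, vaccine naïve participants will be recruited") and in section 10.4 ("If insufficient (<5) participants who received placebo in Study MVX0002 return to this study").
- Without one, in the synopsis ("If an insufficient number of previous placebo recipient participants return to this study, vaccine naïve participants will be recruited") and in inclusion criterion 1 of section 10.4.1, which requires MVX0002 participation "unless it is necessary to recruit vaccine naïve participants to bolster the number of participants who received placebo in MVX0002".

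Section 10.5.4 applies the same range to completers: "A minimum of 30 and maximum of 40 female participants are required to complete the study". On replacement it says: "Participants who withdraw from the study before receiving any IMP will be replaced if suitable reserves are available". Most withdrawals after dosing are decided individually, and withdrawals for significant drug-related adverse events are not replaced.

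**The concern.** The minimum and the trigger stand in adjacent sentences, yet they protect different numbers. Thirty follows from 20 vaccinated women only if the comparator group is full at 10, whereas the trigger acts only below 5. A site with 20 vaccinated women and 5 placebo returnees could conclude that no naïve women may be added and stop at 25. Below 5 returnees the trigger fires, but no section says how many naïve women to add.

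The comparison with placebo/naïve women is part of the primary and secondary objectives and of the Day 85 ANOVA, so the size of that group bears on precision. Section 10.5.4 appears to tighten the requirement further by asking for 30 completers where section 10.9.5 asks for 30 recruited.

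**Working it through.** **Inputs** (section 10.9.5): vaccinated women v = 20 to 30; placebo returnees p = 0 to 10; total 30 to 40; trigger p < 5. I read the limit of 10 as applying to placebo and naïve women together.

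**The plan's own figures.** Maximum: 30 + 10 = 40. Minimum: 20 + 10 = 30, which needs a full comparator group.

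**Trigger not fired (p = 5 to 10).** There are 11 × 6 = 66 combinations. The lowest total is 20 + 5 = 25. Those with v + p < 30 are:

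| p | v | Combinations |
|---|---|---|
| 5 | 20–24 | 5 |
| 6 | 20–23 | 4 |
| 7 | 20–22 | 3 |
| 8 | 20–21 | 2 |
| 9 | 20 | 1 |

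That makes 15, with shortfalls of 1, 2, 3, 4 and 5 women in 5, 4, 3, 2 and 1 of them. The other 51 already reach 30. These are counts of combinations, not probabilities.

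**Can all the stated limits be met together?** Let x be the number of naïve women needed for at least 5 comparators and at least 30 in total:

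x = max(5 − p, 30 − v − p, 0)

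- The comparator group is then p + x = max(5, 30 − v, p). Since v ≥ 20 and p ≤ 10, it never exceeds 10.
- The total is v + p + x = max(v + 5, 30, v + p), which lies between 30 and 40.

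This holds in all 11 × 11 = 121 combinations. For p ≥ 5, x is 0 in 51 cases and 1 to 5 in 15. For p < 5, it runs from 1 (p = 4, v ≥ 25) to 10 (p = 0, v = 20). The rules conflict only if the trigger is read as the sole permission to recruit naïve women.

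**Is it the sole permission?** Sections 10.1, 10.4 and 10.9.5 say what happens if fewer than 5 return. None says only if. Eligibility is governed by inclusion criterion 1, which turns on necessity and gives no number.

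**Precision.** The protocol gives no standard deviation, so I assume 1.0 on the natural-log scale (range 0.8 to 1.2) and simplify to two groups, pooled vaccinated women against comparators. The 95% CI for the Day 85 geometric mean ratio is the estimate divided and multiplied by exp{t(0.975, v + c − 2) × SD × √(1/v + 1/c)}, where c is the number of comparators:

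- v = 20, c = 5: t = 2.069, √0.25 = 0.500, factor 2.81 (2.29 to 3.46)
- v = 25, c = 5: factor 2.73 (2.23 to 3.33)
- v = 20, c = 10: t = 2.048, √0.15 = 0.387, factor 2.21 (1.89 to 2.59)

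Raising the total from 25 to 30 with vaccinated women barely changes the interval; filling the comparator group narrows it. The total of 30 is thus not what fixes precision, and the protocol expressly allows fewer than 10 placebo returnees.

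**Recruited against completing.** Recruiting 31 to 40 women with at least 30 completing satisfies both sections. A conflict needs exactly 30 recruited and one withdrawal that is not replaced, which leaves 30 − 1 = 29.

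**The case for a change.** The strongest argument for a change is that the pool can run dry. Section 10.4 has every MVX0002 participant re-contacted, and section 10.9.5 concedes that willingness limits the size. If that pool is exhausted at 25 to 29 women, naïve women are the only source left. Three sections put the number 5 on what counts as insufficient, and section 10.4 allows no deviation from the eligibility criteria. A cautious site could then feel bound to miss the minimum. This is recruitment and eligibility content, so it cannot be left to a statistical analysis plan.

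Part of this stands. The synopsis and criterion 1 lack the threshold that the other sections carry, and nowhere is a target for the comparator group given. The rest does not hold. A site at 25 to 29 has an unmet requirement of at least 30, and criterion 1 lets naïve women in where that is necessary to strengthen the placebo group. Enrolling them is within the criterion and is not a deviation from it. Nor is the number to add wholly open: the threshold implies at least 5 comparators, the minimum implies at least 30 − v, and the upper limits close the range.

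**Conclusion.** No change to the plan is needed. The arithmetic behind the concern is right: the trigger alone guarantees 20 + 5 = 25, and 15 of 66 combinations fall 1 to 5 women short of 30. But the trigger is not the rule that secures the total. The minimum of 30 does that, and the two can be met together in every in-range combination. A sponsor following the text reaches 30.

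The remaining points are a threshold missing from the synopsis, an unstated comparator target and a loose use of recruited and completing. They are gaps of detail that the study team can settle sensibly during recruitment. No stated power rests on the 30, the within-participant comparisons with MVX0002 do not depend on the number of naïve women, and no planned analysis would be done differently.

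This rests on reading the trigger as a sufficient condition and on applying the limit of 10 to placebo and naïve women together. The precision figures also assume the log-scale standard deviation given above.
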